5.1.2. Analysis change from baseline of QTc (Δ QTc) in apalutamide

- The change from baseline in QTc (Δ QTc) intervals at each time point will be listed for each subject and treatment. For each treatment and time point of measurement, the change from baseline in QTc intervals (Δ QTc) will be summarized using descriptive statistics (mean, SD, median, range).
- A repeated-measures mixed model will be fitted with change from baseline in QTc (ΔQTc) as the dependent variable, and treatment (Apalutamide vs. Placebo), time point of measurement, and treatment by time point of measurement interaction as fixed effects, baseline value of QTc as covariate, and subject as a random effect. Using the estimated least square means and intra-subject variance from the model, 2-sided 90% CI for mean ΔQTc of apalutamide active treatment group at each time point will be constructed. The incidence count and percentage of subjects with QTc increase >30 to ≤60 and >60 msec will be summarized for each treatment group. The incidence count and percentage by time point will also be summarized for each treatment group. Subjects with QTc increase >60 msec will be listed.
- Mean change from baseline in QTc intervals (Δ QTc) versus time profiles for both treatments will be plotted on the same graph.

5.1.3. Analysis of the difference between apalutamide and placebo in \triangle QTc ($\triangle \triangle$ QTc)

- The treatment difference in mean (SD) of ΔQTc between apalutamide and placebo will be calculated at each matched time point.
- A repeated-measures mixed model will be fitted with ΔQTc as the dependent variable, and treatment (apalutamide vs. Placebo), time point of measurement, and treatment by time point of measurement interaction as fixed effects, baseline value of QTc as covariate, and subject as a random effect. Using the estimated least square means and intra-subject variance from the model, 2-sided 90% CI for the difference in mean ΔQTc between apalutamide and placebo at each time point will be constructed.

5.1.4. Analysis of the relationship between QT/QTc and RR at baseline

- The relationship between QT/QTc and RR at baseline will be evaluated graphically by plotting the logarithm of baseline QT/QTc values against the logarithm of corresponding RR intervals.
- A linear regression model will be fitted to the data with logarithm of baseline QT/QTc interval values as the dependent variable and logarithm of RR as the predictor. The slope of the regression line and its standard error, along with 2-sided 95% confidence intervals for the slope, will be estimated from this model.

Statistical Analysis Plan ARN-509-003 QT Study

5.2. Heart Rate (HR)

Mean HR over time will be listed for each subject and treatment. For each treatment and time point of measurement, HR will be summarized using descriptive statistics (mean, SD, median, range).

Mean change from baseline in HR will also be summarized using descriptive statistics (mean, SD, median, range) for each treatment group and time point.

A repeated-measures mixed model will be fitted with Δ HR as the dependent variable, and treatment (Apalutamide vs. Placebo), randomization stratification criteria, time point of measurement, and treatment by time point of measurement interaction as fixed effects, baseline value of HR as covariate, and subject as a random effect. Using the estimated least square means and intra-subject variance from the model, 2-sided 90% CI for the difference in mean Δ HR between apalutamide and placebo at each time point will be constructed.

The number and percentage of subjects with any postdose heart rate >100 bpm and <50 bpm will be summarized by treatment group and by time point.

To investigate any effect of treatment on heart rate, a mean plot for change from baseline in heart rate (Δ HR) over time by treatment group (on the same page) will be presented.

5.3. QRS and PR intervals

Mean QRS and PR intervals will be listed for each subject and treatment. For each treatment and time point of measurement, QRS and PR intervals will be summarized using descriptive statistics (mean, SD, median, range).

Mean change from baseline in QRS and PR intervals will also be summarized using descriptive statistics (mean, SD, median, range) for each treatment group and time point.

A repeated-measures mixed model will be fitted with ΔQRS (or ΔPR) as the dependent variable, and treatment (Apalutamide vs. Placebo), time point of measurement, and treatment by time point of measurement interaction as fixed effects, baseline value of QRS (or PR) as covariate, and subject as a random effect. Using the estimated least square means and intra-subject variance from the model, 2-sided 90% CI for the difference in mean ΔQRS (or ΔPR) between apalutamide and placebo at each time point will be constructed.

The number and percentage of subjects with QRS interval >120 msec will be summarized for each treatment group. The incidence count and percentage by time point will also be summarized.

The number and percentage of subjects with PR interval >200 msec will be tabulated for each treatment group.

Statistical Analysis Plan ARN-509-003 QT Study

5.4. Changes in T Wave Morphology

The incidence of subjects with changes in T-wave morphology from baseline will be tabulated by coded descriptive T-wave morphology and by treatment group. The codes of descriptive T-wave morphology (based on ECG Chapter of this sub-study) are listed in the following table:

Code for Descriptive	Description
T Wave Morphology	
Normal T waves	always upright in leads I, II, V5 and V6 and always negative in aVR.
Peaked T-waves	one or more T wave appears abnormally tall and sharp
Flat T-waves	one or more T wave appears flatter than normal
Notched T-waves	one or more T wave is notched (possibly due to T/U fusion) but remains of
	one polarity
Bi-phasic T-waves	one or more T wave has a both a negative and a positive component
Inverted T-waves	one or more T wave that should normally be positive is inverted

In the calculation of the incidence, all abnormal changes in T wave morphology based on any lead (e.g., primary lead, backup lead, and/or other leads) and at any post-baseline time-points should be counted.

6. PHARMACOKINETIC/PHARMACODYNAMIC RELATIONSHIPS

The evaluation of PK/PD relationship will be performed using data from all subjects who received the active drug and have ECG data from at least one time point following the first dose.

- The following plots will be generated to evaluate the relationship between mean and mean change in QTc intervals and plasma concentrations of apalutamide:
 - QTc at each time point of measurement will be plotted against the corresponding plasma concentration of apalutamide.
 - ΔQTc at each time point of measurement will be plotted against the corresponding plasma concentration of apalutamide.

Additional plots will be produced, if deemed necessary.

- For active treatment group apalutamide, the change from baseline in QTc intervals at the individual subject's apalutamide plasma concentrations on Cycle 3 Day 1 (i.e. predose, 2 hr postdose, 4 hr postdose) will be summarized using descriptive statistics mean, SD median, and range.
- Linear mixed effects model will be fitted to the ∆QTc data with apalutamide concentration as a predictor and subject as a random effect (random intercept and random slope model); if the intercept term is not significant, the model will be re-fitted with a zero intercept term. The analyses above will be repeated for principal metabolite (JNJ-56142060).
- Outliers of individual drug concentrations will be identified by pharmacokineticist. If deemed necessary, the above analyses will be repeated with no outliers.

ARN-509	Statistical Analysis Plan ARN-509-003 QT Study
REFERENCES	

- E14 Clinical Evaluation of QT/QTc Interval Prolongation and Proarrhythmic Potential for Non-Antiarrhythmic Drugs. Guidance for Industry. U.S. Department of Health and Human Services, Food and Drug Administration, Center for Drug Evaluation and Research, Center for Biologics Evaluation and Research, ICH. Oct 2005.
- 2. Fridericia, L. S. (1920). Die Systolendauer im Elektrokardiogramm bei normalen Menschen und bei Herzkranken. Acta Medica Scandinavica, Stockholm. 57: 469-486
- 3. Bazett HC. An analysis of the time-relationship of electrocardiograms. Heart 1919;70:353-370.

Patient Reported Outcomes (PRO) Statistical Analysis Plan (SAP)

SPARTAN

(Selective Prostate AR Targeting with ARN-509)

A Multicenter, Randomized, Double-Blind, Placebo-Controlled, Phase III Study of ARN-509 in Men with Non-Metastatic (M0) Castration-Resistant Prostate Cancer

ARN-509-003; Phase 3

Sponsor:

Aragon Pharmaceuticals, Inc*

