**Statistical Methods**

A detailed Statistical Analysis Plan will be prepared prior to the planned analyses.

Two analyses will be performed: a primary analysis using the active treatment arm only, and a secondary analysis comparing the active and placebo arms, both accompanied by a pharmacokinetic/pharmacodynamics analysis.

Standard ECG parameters will be determined for each ECG recording. Corrected QTc intervals will be determined using Fridericia's formula (QTcF) and Bazett's formula (QTcB).

Changes in ECG intervals from baseline will be calculated. Baseline will be defined as the mean of the values for the triplicate ECG measurements taken pre-dose on Cycle 1 Day 1 (Hour -1 and Hour 0). In addition, QTcFs will be categorized based on ICH E14 guidelines. Tables will present the number and percentage of patients meeting or exceeding the following categories:

- QTc interval prolongation:
  - Absolute values  $> 450$  to  $\leq 480$  msec
  - Absolute values  $> 480$  to  $\leq 500$  msec
  - Absolute values  $> 500$  msec
- QTc interval change from baseline:
  - Increase from baseline  $> 30$  to  $\leq 60$  msec
  - Increase from baseline  $> 60$  msec

Pharmacokinetic/Pharmacodynamic analyses will be performed using data from all subjects who have ECG data from at least one time point following the first dose. A linear modeling approach will be used to quantify the relationship (if any) between the plasma concentration of drug (apalutamide) and its principal metabolite (ARN000308), and the changes from baseline in the QTcF interval.

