#### **Statistical Assumptions**

The standard deviation of the change from baseline at each time point is assumed to be 20 msec. The magnitude of the true QTcF prolongation in the secondary analysis (i.e., the expected value of  $\Delta\Delta$ QTcF) is taken as 5 msec. For the primary analysis, an allowance should also be made for possible diurnal variation etc., so results are presented assuming the true value of  $\Delta$ QTcF is 8 msec and 10 msec.

The power calculations have been performed by looking at various possible sample sizes and deriving the resulting power for the analysis at a single time point. However, in order for the study to be declared negative, the upper confidence limit has to be below the threshold at all on-study time points. If the results at each on-study time point were uncorrelated, a power of about 98% at each individual on-study time point would be required to give an overall power (i.e., to achieve the desired result at all on-study time points) of 80%. Similarly, a 99% power at each individual on-study time point would give an overall power of about 90%. However, some correlation between the time points is expected to be present, therefore, the goal is to aim for a power (for an individual time point) well in excess of 95% in order to achieve a reasonable overall power.

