1.4.2. Achieved Sample Size and Change in Planned Analysis

As a consequence of slow patient's enrollment to the QT substudy, approximately 17 subjects were randomized by the clinical cutoff date, which is only 17% of the originally planned sample size. To be consistent with this change, no hypothesis testing will be performed and all planned statistical analysis in the QT substudy will be performed for an estimation purpose.

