2.5. Analysis Sets

PD Analysis Set

Pharmacodynamics (PD) analysis set will include all subjects from the sub-study who were randomized and received at least one dose of the study drug and had both predose and at least one postdose ECG measurement.

PD analysis set will be used for all ECG-related analysis (include Subject Information).

PK Analysis Set

The Pharmacokinetic (PK) analysis set will include all subjects from the sub-study who were randomized and received at least one dose of the study active drug and have estimable PK parameter Cmax. This analysis set combined with Pharmacodynamics (PD) analysis set will be used for PK/PD relation analysis.

Subjects who received placebo will not be part of the PK population.

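### The QT sub-study's secondary concentration-QTc model is refitted through zero on a weak test and leaves out placebo, so a modest non-drug QTc shift can be partly read as drug effect

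*SAP*

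**What the plan says.** The ventricular repolarization sub-study SAP (QT SAP), section 6, fits change from baseline in QTc on apalutamide concentration, with "subject as a random effect (random intercept and random slope model"). It then adds that "if the intercept term is not significant, the model will be re-fitted with a zero intercept term". No significance level is given for that test, and the text does not say whether the random intercept stays in the refit. The metabolite is handled the same way.

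The data are limited to "all subjects who received the active drug and have ECG data from at least one time point following the first dose". Section 2.5 agrees: "Subjects who received placebo will not be part of the PK population". Protocol Appendix 8, Statistical Methods, is wider. There the PK/PD "analyses will be performed using data from all subjects who have ECG data from at least one time point following the first dose", and both the active-only and the active-versus-placebo analysis are to be accompanied by PK/PD.

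Section 1.4.2 reports that "approximately 17 subjects were randomized by the clinical cutoff date" and turns every planned QT analysis into estimation without hypothesis testing.

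The protocol expects some non-drug change. Appendix 8, Statistical Assumptions, takes 5 msec as the placebo-corrected effect but 8 or 10 msec for the uncorrected change in the active arm, because "an allowance should also be made for possible diurnal variation". The criteria for a negative result name the placebo contrast as the means of removing diurnal and time-on-study change.

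**The concern.** A non-significant intercept in about 11 patients is weak evidence that the intercept is zero. If QTc moves for reasons unrelated to drug, a line forced through the origin has to account for that movement with its slope. The slope is then wrong, and its interval is too narrow because it takes the intercept as known.

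The active-only restriction makes this harder to see. At Cycle 1 Day 1 concentrations are low and at Cycle 3 they are near steady state, so in active patients concentration and visit are almost the same variable. Placebo patients, whose ECGs follow the same schedule, are the only ones who show what QTc does over that period without drug. The QT SAP gives no reason for leaving them out of this model.

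There is also a tension inside the QT SAP: section 1.4.2 removes hypothesis testing, yet section 6 lets a significance test choose the model. What is at stake is the accuracy of the slope under one of the sub-study's secondary objectives.

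**Working it through.** **The plan's own figure.** Appendix 8 uses SD 20 msec, threshold 20 msec, one-sided 0.05, 60 active patients and a true change of 10 msec. Power = Phi((20 - 10)/(20/sqrt(60)) - 1.645) = Phi(2.23) = 98.7%, as stated. The rest of both power tables also reproduces. The documents give no figure for the concentration-QTc model.

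**Inputs from the documents.** Active patients: 17 x 2/3 = 11.3, taken as 11. Total SD 20, so variance 400. Non-drug shift: 8 - 5 = 3 to 10 - 5 = 5 msec. Reference concentration 7.55 ug/mL, the mean steady-state Cmax at 240 mg/day (Protocol 1.1.2). Five post-dose ECG times: Cycle 1 at 2 and 4 h; Cycle 3 at 0, 2 and 4 h.

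**Assumptions.** Concentrations 1.5 to 2.5 ug/mL at Cycle 1, and 5, 7.55 and 7.0 at Cycle 3. Between/within-patient variance 100/300, 200/200 or 300/100. No random slope variance. Intercept tested at two-sided 0.05. True drug effect zero.

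**One case in full** (Cycle 1 at 1.5, split 100/300, constant 5 msec shift). Let b and w be the between and within variances, and D = w + 5b = 800.
- Sum of C = 22.55; sum of C squared = 135.50.
- Information terms per patient: 5/800 = 0.00625; 22.55/800 = 0.02819; (135.50 - 100 x 22.55^2/800)/300 = 0.2398.
- SE of intercept = sqrt(0.2398/[11 x (0.00625 x 0.2398 - 0.02819^2)]) = 5.56 msec.
- d = 5/5.56 = 0.90. Chance that the intercept is dropped = 1 - Phi(0.90 - 1.96) - Phi(-0.90 - 1.96) = 85%.
- The refitted slope equals the original slope plus k times the fitted intercept, with k = 0.02819/0.2398 = 0.1176. Expected refit reading at 7.55 = 7.55 x 0.1176 x 5 = 4.4 msec.
- Averaged over all trials under the rule it is smaller, because the intercept is dropped when its estimate happens to be small: 5.56 x {0.90 x 0.853 - [0.2275 - 0.0067]} = 3.04, and 7.55 x 0.1176 x 3.04 = 2.7 msec.

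**Range over the assumptions**

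| Constant shift | Dropped, 11 active | Dropped, 60 active | Refit reading at 7.55, random intercept kept | Refit reading, random intercept dropped too |
|---|---|---|---|---|
| 3 msec | 92-93% | 76-81% | 0.8-3.1 msec | 3.8-3.9 msec |
| 5 msec | 85-88% | 44-57% | 1.3-5.1 msec | 6.3-6.5 msec |

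The SE of the intercept at 11 patients is 5.6 to 6.6 msec. Mixed-model fits to simulated data (200 runs per setting) dropped the intercept in 90-93% (3 msec) and 82-85% (5 msec).

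**Rule against remedy, by simulation** (11 active, 6 placebo, SD 20, intraclass correlation 0.3 or 0.6, constant 3 to 5 msec shift, random subject intercept kept). Under the rule the intercept was dropped in 86-93% of runs, average bias at 7.55 was 0.9 to 2.7 msec, and a nominal 90% slope interval covered 74-87%. With the intercept always kept and placebo at zero concentration, bias was near zero and coverage about 90%. Root mean square error was 4.7-5.7 against 4.8-6.7 msec under the rule with one set of assumed concentrations, and 5.1-6.0 against 5.0-7.2 with another.

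**A 5 msec shift present only at Cycle 3.**
- Active patients only, intercept kept: 6.7 to 7.9 msec read as drug effect. Refit through zero: 5.7 to 7.1.
- Intercept kept and placebo at zero, no visit term: 2.6 to 6.5 msec remains, depending on the assumed concentrations.
- Adding a Cycle 1/Cycle 3 term removes it. The SD of the estimate at 7.55 rises from about 4.7-5.6 to about 6.5-7.1 msec.

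**The case against.** The strongest reply is that little depends on this model. The primary variable is the change in QTcF, and concentration-QTc is one of several secondary objectives. QT SAP section 5.1.3 keeps placebo and gives 90% intervals for the placebo-corrected change at each time point, which is where the protocol assigns removal of non-drug change. The average bias of about 1 to 3 msec is below the estimate's own SD and far below 20 msec, and an upward shift errs towards overstating a QT effect. All of this stands and limits the weight.

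Three stronger readings are tempting, and the documents do not support them.
- A reader might infer that any non-drug shift ends up in the slope. A shift large enough to be significant keeps its intercept, and a random intercept retained in the refit absorbs part of the rest.
- A reader might take the predicted effect at peak concentration as the sub-study's key output. Section 6 specifies neither such a prediction nor an interval; 7.55 ug/mL and the 90% interval are used here only to express size.
- A reader might take Appendix 8 as already setting placebo concentrations to zero, or placebo as discarded altogether. Appendix 8 says only which patients enter, and placebo is left out of this model, not of the sub-study.

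It is also fair that a constant shift is the convenient case. Diurnal and time-on-study change need not be constant over the five times, and for a shift that arises late, keeping the intercept and adding placebo is not enough. That is a reason to extend the remedy, not to keep the rule. The reply does not defend choosing the model by a test that cannot see the shift the protocol expects.

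**Conclusion.** The point holds, with limited weight. With about 11 active patients, the intercept test would miss a constant 3 to 5 msec non-drug shift in about 85-93% of cases. The rule would then report on average about 1 to 3 msec of it as drug effect at 7.55 ug/mL if the random subject intercept is kept. If that is dropped too, the refit reading is up to about 6.5 msec. A nominal 90% slope interval would cover about 74-87%. The QT SAP population is also narrower than Appendix 8 without explanation.

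The sizes depend on an inferred 11:6 split, assumed Cycle 1 and Cycle 3 concentrations, an assumed variance split, a 0.05 test level and no random slope variance. The direction does not: forcing a line through zero moves a constant upward shift into the slope. The rule would be weak even at the planned 60 active patients, where a 3 msec shift is missed in 76-81% of cases. Nothing here affects the primary change-from-baseline analysis or the placebo-corrected estimates.

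**What to change.** In QT SAP section 6, for both apalutamide and the metabolite:
- Delete the zero-intercept refit and keep the fixed intercept in every fit. This also settles what happens to the random intercept in the refit.
- Restore the Appendix 8 population by including placebo patients with post-dose ECGs, and state that their concentration is set to zero, since Appendix 8 does not say so. Amend the PK set wording in section 2.5, or define a separate set for this model.
- Add a Cycle 1/Cycle 3 visit term, at least as a sensitivity model, and report the slope with and without it.

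The cost is SAP wording; the ECGs are already scheduled in both arms. For a constant shift, keeping the intercept with placebo costs essentially no precision. The visit term does: the SD at 7.55 ug/mL rises to about 6.5-7.1 from 4.7-5.6 msec, which is why it may sit better as a sensitivity model with so few patients.

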1. INTRODUCTION

This document describes the planned statistical analyses of the PRO measures collected in ARN-509-003 the **SPARTAN** Study (A Multicenter, Randomized, Double-Blind, Placebo-Controlled, Phase III Study of ARN-509 in Men with Non-Metastatic (M0) Castration-Resistant Prostate Cancer). This PRO analysis plan is meant to supplement the study protocol and the study statistical analysis plan (SAP). Any deviations from this analysis plan will be described in the clinical study report.

Study design can be found in the ARN-509-003 protocol and study SAP.

2. METHODS

2.1 PRO TIME AND EVENTS SCHEDULE

Patients will be required to complete two self-administered quality of life instruments: the Functional Assessment of Cancer Therapy-Prostate (FACT-P) and the Euro-QoL Group EQ-5D^{1,Error! Reference source not found.}, according to the schedule below:

Treatment Phase:

- Cycle 1 Day 1 (before dose)
- D1 C1-C6, D1 of every 2 cycles starting at C7 to C13, then D1 of every 4 cycles unless otherwise specified

Posttreatment Phase:

- End of treatment visit
- Long-term Follow-up: every 4 months up to 12 months post progression

Patients will complete the FACT-P and EQ-5D at the clinic during the Treatment Phase PRIOR to any other clinical activity. During Long-term Follow-up contact every 4 months via clinic visit or an alternative contact method per institution policy/practice up to 12 months post progression.

